11.3 Statistical methods

This section provides specifications for preparation of final Statistical Analysis Plan (SAP), which will be issued prior to database lock. Any differences compared to this statistical section should be identified and documented in final SAP. Analysis will be done using SPSS version 21.

Categorical variables will be presented by number and percentage. Chi square test (or its subsidiaries) will be used to determine the p value. P -value <0.05 is considered significant.

Numerical Parametric variables will be presented by mean, SD and range. Paired ttest will be used to determine p-value between before and after treatment. Repeated measure ANOVA will be used to calculate significant effect for each group independently from baseline to end of treatment. One-way ANOVA test will be used to show and determine p-value and significance between 3 treatment groups at each point.

Numerical Non-Parametric variables will be presented by Median and interquartile range. Wilcoxon Sign Rank test will be used to determine p-value between before and after treatment. Friedman test will be used to calculate significant effect for each group independently from baseline to end of treatment. Kruskal-Wallis test will be used to show and determine p-value and significance between 3 treatment groups at each point.

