2 STUDY DESIGN

This is a Prospective, Multi center, open-label, randomized, control, Interventional, phase IV Study will be conducted in 2 sites in Egypt; the Research Center of Air Force Specialized Hospital and Helwan University Hospital to assess the efficacy & safety of Ursoplus® capsules (UDCA 250mg & Silymarin 140mg) versus UDCA alone versus Placebo among compensated Chronic Liver Disease Patients.

This study is a clinical trial that will enroll 297 patients, based on Vibration-controlled transient elastography in screening visit; subjects will be enrolled in 2 groups:

- Group 1: with non-cirrhosis, F0, F1 and F2.
- Group 2: with advanced fibrosis and cirrhosis, F3 and F4

Subjects in each group (1 or 2) will be treated with either:

- Ursoplus[®] capsules (group A),
- Ursofalk® capsules (UDCA 250mg); group B (control group 1):
- Or with Placebo, in group C (control group 2), using Stratified random sampling

Generated by Data Management department (DM) of the CRO (Nagy Research) for the 3 treatment groups with a ratio of 1: 1:1. Subjects who will be enrolled in this study will agree to the release of information and sign an informed consent. Subjects included in this study are enrolled for the collection of data that reflect the care they receive under routine clinical circumstances. All provided care should be according to protocol and the local standard of medical care.

The screening and enrollment period is planned to be 6 months. The total duration of the study/subject will be 6 months for treatment, follow-up, and End of Study visits

3 Inclusion and Exclusion Criteria:

3.1 Inclusion Criteria:

Subjects meeting all of the following criteria will be considered for enrollment in the study:

- 1. Male and female patients aged ≥ 18
- 2. Subjects with Compensated Chronic Liver Disease, defined as child 5-7.
- 3. Patients with mild disturbance of liver biochemical profile by one of the following criteria: (elevated Total Serum Bilirubin ≤ 3 mg/dl, or elevated Direct Serum Bilirubin ≤ 2 mg/dl, or elevated one or more of liver enzymes up to 3 times of the normal level).: (Alanine Transaminase (ALT), Aspartate Aminotransferase (AST), Alkaline Phosphatase (AIP) & Gamma Glutamyl Transpeptidase (GGT)).
- 4. Non-diabetic subjects and subjects with Controlled DM-type 1 and 2 patients, HbA1C up to 7.5%
- 5. Non-pregnant or lactating female patients

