6 ASSESSMENT SCHEDULE

Subjects will be enrolled for duration of 6 months including the screening visit

- Screening visit 1 (Treatment initiation)
- Visit 2: after 1st month, follow-up 1
- Visit 3: after 2nd month, follow-up 2
- Visit 4: after 3rd month, follow-up 3
- Visit 5: after 4th month, follow-up 4
- Visit 6: after 5th month, follow-up 5

7 Determination of Sample Size:

As the primary objective is to assess the efficacy of Ursoplus[®] capsules (UDCA 250mg & Silymarin 140mg) versus UDCA alone versus Placebo among Egyptian NASH Patients in reduction of total serum bilirubin, and based on the previous study of [the hepatoprotective effect of Silymarin and UDCA in CHC patients][i], which have been conducted on 40 patients; 10 patients received silymarin, 10 patients received UDCA, 10 patients received Silymarin + UDCA and 10 patients received Placebo.

And this study showed that:

The 12 weeks treatment period of Placebo did not show significant improvement regarding T Bilirubin levels $1.6 \pm 1.0 \text{ Vs.} 1.8 \pm 0.7$, p=0.166

A statistically significant improvement in mean \pm SD serum T bilirubin levels 1.3 \pm 0.5 vs. 1.2 \pm 0.5, p = 0.016 was obtained with 500mg/day UDCA therapy

In addition, the mean \pm SD; T. bilirubin levels for the combined therapy group (Silymarin + UDCA) decreased significantly 1.4 \pm 0.1 vs. 1.2 \pm 0.3, p= 0.022

Given that a researcher has the null hypothesis that $\mu=\mu 0$ and alternative hypothesis that $\mu=\mu 1\neq \mu 0$, and that the population variance is known as $\sigma 2$. Also, he knows that he wants to reject the null hypothesis at a significance level of α which gives a corresponding Z score, called it $Z\alpha/2$. Therefore, the power function will be

```
P\{Z > Z\alpha/2 \text{ or } Z < -Z\alpha/2|\mu 1\} = 1-\Phi[Z\alpha/2-(\mu 1-\mu 0)/(\sigma/n)]+\Phi[-Z\alpha/2-(\mu 1-\mu 0)/(\sigma/n)].
```

So, the following parameters are used to calculate the expected sample of the study:

Design: F tests - ANOVA: Fixed effects, omnibus, one-way, Analysis: A priori: Compute required sample size

• Input:

o Effect size f = 0.2124591 o α err prob = 0.05 o Power (1- β err prob) = 0.863 o Number of groups = 3

[figure not shown]
Output:

[figure not shown]
Non-centrality parameter λ = 12.1874947
 Critical F = 3.0295971
 Numerator df = 2
 Denominator df = 267

Denominator df
 Total sample size
 Actual power
 267
 270
 0.8697572

- Confidence level 95% (α error = 5%)
- Study Power = 87%

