12.2 Primary End Point

Table 3 Percent change of mean Total serum bilirubin at baseline and after 6 months of treatment

| Total serum bilirubin | Group 1 | | | n volue | | p -value | | |
|----------------------------------|---------|------|---------|-----------------|------|-----------------|---------|-----------------|
| | Urso | UDCA | Placebo | p -value | Urso | UDCA | Placebo | μ -value |
| V1 | | | | | | | | |
| V6 | | | | | | | | |
| % Change | | | | | | | | |
| p -value between V1 & V6 | | | | | | | | |
| p -value between 3 groups | | | | | | | | |

 Table 4
 Percent change of mean direct serum bilirubin at baseline and after 6 months of treatment

| direct serum bilirubin | Group 1 | | | n volvo | | p-value | | |
|---------------------------------|---------|------|---------|-----------------|------|---------|---------|---------|
| | Urso | UDCA | Placebo | p -value | Urso | UDCA | Placebo | ρ-value |
| V1 | | | | | | | | |
| V6 | | | | | | | | |
| % Change | | | | | | | | |
| p -value between V1 & V6 | | | | | | | | |
| p-value between 3 groups | | | - | | | | | |

 Table 5
 Percent change of mean ALT at baseline and after 6 months of treatment

| ALT | Group 1 | | | n volvo | | p -value | | |
|----------------------------------|---------|------|---------|-----------------|------|-----------------|---------|---------|
| | Urso | UDCA | Placebo | p -value | Urso | UDCA | Placebo | ρ-value |
| V1 | | | | | | | | |
| V6 | | | | | | | | |
| % Change | | | | | | | | |
| p -value between V1 & V6 | | | | | | | | |
| p -value between 3 groups | | - | - | | | | | |

Table 6 Percent change of mean AST at baseline and after 6 months of treatment

| AST | Group 1 | | | n volue | | p-value | | |
|----------------------------------|---------|------|---------|-----------------|------|---------|---------|---------|
| | Urso | UDCA | Placebo | p -value | Urso | UDCA | Placebo | μ-value |
| V1 | | | | | | | | |
| V6 | | | | | | | | |
| % Change | | | | | | | | |
| p -value between V1 & V6 | | | | | | | | |
| p -value between 3 groups | | | | | | | | |

 Table 7
 Percent change of mean ALP at baseline and after 6 months of treatment

| ALP | | Group 1 | | p -value | | p -value | | |
|----------------------------------|------|---------|---------|-----------------|------|-----------------|---------|---------|

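### Within-arm before-after p-values sit beside the between-arm test in the primary tables, the SAP does not say which one decides efficacy, and regression to the mean may make an ineffective arm look improved

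*SAP*

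**What the plan says.** SAP 11.3 sets out two kinds of test for numerical variables.

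- **Within each arm.** "Paired ttest will be used to determine p-value between before and after treatment", with the Wilcoxon test as the non-parametric version. In addition, "Repeated measure ANOVA will be used to calculate significant effect for each group independently from baseline to end of treatment", with Friedman as its counterpart.
- **Between arms.** One-way ANOVA or Kruskal-Wallis across the three treatment groups at each time point.

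One threshold covers everything: "P -value <0.05 is considered significant".

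The shells for Tables 3-8 (total and direct bilirubin, ALT, AST, ALP, GGT) carry both kinds. One p-value row is labelled "value between V1 & V6" and the next compares the three groups. Both appear for each fibrosis stratum.

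On entry, SAP 3.1 admits "Patients with mild disturbance of liver biochemical profile by one of the following criteria": raised total bilirubin, raised direct bilirubin, or one or more of four raised enzymes. Enzymes more than three times normal are excluded (SAP 3.2). SAP 6 makes the screening visit also the start of treatment. The protocol CRF has one laboratory panel before randomisation and the next at end of study, so the value that qualifies a patient is also the baseline.

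**The concern.** A patient chosen because a lab is high today will, on average, have a lower value next time without any treatment. A paired test within one arm cannot separate that fall from a drug effect. Finding a significant fall in one arm and none in another is also not a comparison of the arms.

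Three features of the SAP make misuse easy.

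- SAP 11.4.1 states the primary analysis (percent change in the six labs) without naming a test or a contrast.
- The between-arm test in 11.3 is described at each time point. As worded, the tests there that address change are the within-arm ones.
- The ANOVA is an omnibus test. If it is significant, a reader still has to ask which arm differs, and the within-arm p-values stand ready as an answer.

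The sample-size section already summarises its source study this way, setting a non-significant before-after result for placebo (p=0.166) beside significant ones for UDCA (p=0.016) and the combination (p=0.022).

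At stake is an efficacy claim for Ursoplus that rests on within-arm falls and not on the randomised comparison.

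**Working it through.** **1. What the plan's own calculation tests.** SAP 7 uses "Design: F tests - ANOVA: Fixed effects, omnibus, one-way" with "Effect size f = 0.2124591".

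- The planning changes in total bilirubin are +0.2 (placebo), -0.1 (UDCA) and -0.2 (combination). Their mean is -0.0333 and their SD (divisor 3) is sqrt(0.08667/3) = 0.16997.
- 0.16997/0.2124591 = 0.80, so the implied SD is 0.8 mg/dl.
- λ = f² x N = 0.2124591² x 270 = 12.1875, with critical F 3.0296 on 2 and 267 df. All match the SAP.
- Power from the non-central F is 0.885, against the stated 0.870. The gap has no bearing here.

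So the trial was sized for a comparison of change between arms.

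**2. Number of within-arm tests.** 6 x 3 x 2 = 36. With no effect and no regression to the mean, each has a 2.5% chance of a significant fall. For six independent labs in one arm, the chance of at least one is 1 - 0.975^6 = 14%. With only two laboratory time points, repeated-measures ANOVA repeats the paired t-test (F = t²).

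**3. Bilirubin on the plan's scale.** With an SD of change of 0.8, a fall reaches p<0.05 at 1.987 x 0.8/√90 = 0.168 mg/dl (arm of 90) or 2.015 x 0.8/√45 = 0.240 mg/dl (cell of 45). A regression fall of 0.2 mg/dl would be significant in 65% or 37% of trials. A fall of 0.1 would be significant in 22% or 13%. The 45 assumes that 90 evaluable patients per arm split equally between strata.

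**4. Upper case: every analysed patient selected on the lab tested.** Assume a standard normal lab, retest correlation r and entry above +0.5 SD.

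- Expected fall = (1-r) x φ(0.5)/[1-Φ(0.5)] = (1-r) x 1.141: 0.342 SD at r=0.7 and 0.114 SD at r=0.9.
- Variance of change = (1-r)² x 0.269 + (1-r²), giving SDs of 0.731 and 0.439.
- For n=90, t is centred at 4.44 and 2.46, so P(significant fall) ≈ Φ(4.44-1.987) = 99% and Φ(2.46-1.987) = 68%.
- For n=45 the same steps give 87% and about 40%.

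**5. Entry on any one of six labs, as SAP 3.1 states.** This was simulated with no treatment effect. Assumptions: inter-lab correlation 0.3, r = 0.7-0.9, and all six labs capped. The answer also depends on whether short-term fluctuations are shared between labs (correlation 0.3) or independent, with only long-term levels correlated. Chance of a significant fall per lab:

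| Entry cut / cap (SD) | Shared, n=90 | Shared, n=45 | Independent, n=90 | Independent, n=45 |
|---|---|---|---|---|
| +0.5 / +3 | 7-12% | 5-8% | 4-5% | 3-4% |
| +1 / +2 | 9-19% | 6-11% | 4-6% | 3-5% |
| +1.64 / +3 | 30-70% | 17-41% | 8-17% | 6-11% |

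Seven per cent is not a floor. A cut of +0.5 with a cap of +2 gives 4-6% (shared, n=90), and a very tight cap (cut at the mean, cap +1) takes the rate below 2.5%.

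**6. Half the patients raised on the lab** (cut +0.5, the rest truly below it): 9-19% for n=90 and 6-10% for n=45.

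**7. The between-arm test in the same simulations.** One-way ANOVA of change rejects in about 3-7% of runs, which is 5% within simulation noise.

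**The case against.** The strongest reply is that the plan already contains the right test. SAP 11.3 names a between-arm ANOVA or Kruskal-Wallis, each primary table has a row for it, SAP 5.1 words the primary endpoint between three groups, SAP 11.4 speaks of comparing study treatment with two controls, and the sample size is a between-group ANOVA. All of that stands. A reader might infer that the primary analysis is only before versus after; the documents do not support that. The gap is that no sentence makes the between-arm result decisive.

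A reader might also infer that placebo is bound to look effective. That does not follow either. Entry needs only one of six raised labs, and the enzymes are capped, so selection on any one lab is diluted. The SAP's only placebo figures show bilirubin rising from 1.6 to 1.8. They come from ten patients over 12 weeks and cover one of six labs, so they are weak evidence, but they point the other way.

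Finally, patients are not selected on steatosis or quality of life, so the mechanism does not reach Tables 9-11 directly. For those tables only the simpler objection remains: a within-arm p-value does not compare arms.

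**Conclusion.** The point holds as a gap in the SAP. Thirty-six within-arm p-values at an unadjusted 0.05 share the primary tables with the randomised test, the selecting value is the baseline, and the SAP does not say which p-value decides. Regression to the mean may make an ineffective arm show a significant fall. The between-arm comparison of change is not biased by it.

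The size is uncertain because the documents give neither retest correlations nor the share of patients raised on each lab. With any-one-of-six entry and the assumptions in the table, the chance per lab is roughly 7-70% (n=90) and 5-41% (n=45) if short-term fluctuations are shared between labs, and about 4-17% and 3-11% if they are independent. It reaches about 70-99% (n=90) only if every analysed patient was selected on that lab. The reference to elevated enzymes in SAP 5.1 would allow such a subset but does not settle it. The fault should be corrected, but it does not undermine the design.

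**What to change.** - In SAP 11.3 and 11.4.1, state that efficacy conclusions rest only on the between-arm comparison of change from baseline to end of study. Word the between-arm test as a test of that change, not only of values at each time point.
- In Tables 3-8, delete the within-arm p-value row and show each arm's change with a 95% CI, labelled descriptive. Remove the paired t, Wilcoxon, repeated-measures ANOVA and Friedman tests as evidence of efficacy.
- In Tables 9-11, label the within-arm results as descriptive.

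The cost is wording and table shells, with no new data or patients. SAP 11.3 foresees a final SAP before database lock, which is the place for it. The downside is that the report loses some favourable-looking within-arm p-values.

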11.4 Analyses variables

The following variables will be analyzed by the overall sample, comparing study treatment versus 2 controls in the 2 groups: non-Cirrhotic liver and advanced Fibroitc & Cirrhotic liver.

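### Efficacy Tables 3-11 test the three arms separately in F0-F2 and F3-F4, with no overall comparison, stratum-adjusted comparison or treatment-by-stratum test shown

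*SAP*

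**What the plan says.** **Randomisation (SAP 8).** Patients are stratified by elastography into Group 1 (F0-F2) and Group 2 (F3-F4), with three arms at 1:1:1. No quota or expected split between the strata is given.

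**Sample size (SAP 7).** The design is "F tests - ANOVA: Fixed effects, omnibus, one-way" with "Effect size f = 0.2124591", "Number of groups = 3" and alpha 0.05. It gives 270 patients at a stated power of 0.8697572, raised to 297 for dropout. The rationale concerns total serum bilirubin. Strata play no part in the calculation.

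**Methods (SAP 11.3).** The between-arm tests for numerical variables are one-way ANOVA or Kruskal-Wallis, and "P -value <0.05 is considered significant". No listed method has a stratum term. The Protocol text consists of case report form pages and adds no analysis method.

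**Variables (SAP 11.4).** The sentence begins by saying the variables are analysed by the overall sample, then continues with "comparing study treatment versus 2 controls in the 2 groups: non-Cirrhotic liver and advanced Fibroitc & Cirrhotic liver".

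**Table shells (SAP 12.2 and 12.3).** Tables 3-8 (the six liver tests), 9 (steatosis) and 10-11 (RAND-36) each set Group 1 beside Group 2. Each block has three arm columns, its own p-value column and a row labelled "p -value between 3 groups". No shell has an overall column or an interaction p-value.

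**The concern.** The trial is powered for one test on the whole sample, but the shells display two tests on parts of it. Two problems follow.

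First, the comparison that the sample size supports has nowhere to appear, and the stratum used in randomisation is not adjusted for in any listed method.

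Second, a reader given two p-value columns side by side will compare them. A p-value below 0.05 in one stratum and above it in the other is not evidence that the effect differs. With reduced power in each part, this pattern is common even when the true effect is the same. The smaller stratum is the likelier one to miss significance, and the plan does not control which stratum that is or how small it becomes. A difference between non-cirrhotic and advanced disease could then be read into results that contain none.

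**Working it through.** **Inputs.** From SAP 7: f = 0.2124591, alpha 0.05, three arms, 270 evaluable. From SAP 11.3: a 0.05 threshold for each p-value. Assumed, because the documents give no figure: stratum splits from 50:50 to 80:20, and the same true f in both strata.

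**Step 1: the SAP's own figure.** For a one-way ANOVA, lambda = f² × N, the critical value is the 95th percentile of F(2, N-3), and power is the probability that a non-central F(2, N-3, lambda) exceeds it. At N = 270, lambda = 0.2124591² × 270 = 12.1875 and the critical F is 3.0296. Both match the SAP. Power comes to 0.885 (0.884 in a 200,000-run simulation) against the stated 0.870. The gap of 1.5 points does not affect what follows.

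**Step 2: the same test within each stratum.** The strata contain different patients, so their tests are independent. With powers p1 and p2:

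- exactly one significant = p1(1 - p2) + p2(1 - p1)
- both significant = p1 × p2

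| Split of 270 | p1 | p2 | Exactly one | Both | Neither |
|---|---|---|---|---|---|
| 135/135 | 0.581 | 0.581 | 49% | 34% | 18% |
| 180/90 | 0.717 | 0.409 | 54% | 29% | 17% |
| 216/54 | 0.799 | 0.254 | 65% | 20% | 15% |

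For 180/90: 0.717 × 0.591 + 0.409 × 0.283 = 0.424 + 0.116 = 0.540.

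If all 297 patients were analysed, exactly one stratum would be significant in 47% (150/147) to 65% (237/60) of trials.

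**Step 3: sensitivity to f.** N = 270, splits from 50:50 to 80:20:

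| True f in both strata | Exactly one significant |
|---|---|
| 0.15 | 43-49% |
| 0.2124591 | 49-65% |
| 0.26 | 36-62% |
| 0.32 | 15-48% |
| 0.40 | 2-27% |

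If no arm differs in either stratum, the figure is 2 × 0.05 × 0.95 = 9.5%.

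**Step 4: what an interaction test would do.** Both strata were simulated with the same true effect (f = 0.2124591, N = 270, 20,000 runs) and a 2-df arm-by-stratum F test at 0.05 was added. It rejected in 5.0% of trials at 135/135 and 5.1% at 189/81. The separate tests disagreed in 49% and 57% of the same trials. Among the disagreeing trials, the interaction was significant in only 7% and 6%.

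**The case against.** The strongest reply is that the plan does intend an overall analysis: SAP 11.4 says so, and the sample size is built on one. A reader who looks only at the tables might infer that no overall comparison is planned, and the text does not support that. What stands is the mismatch: the overall analysis is promised in a phrase and has no place in any efficacy shell. An overall test also could not show whether the effect differs by stage.

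A reader might also infer that the sponsor plans to claim different effects by fibrosis stage. No objective or endpoint says this; SAP 1 and 5 compare treatments without reference to strata. The harm is a foreseeable misreading of the tables, not a stated inference.

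Three limits on the figures are fair:

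- They describe a significant three-arm omnibus F. It would be wrong to read that as the product looking effective in a stratum, because a UDCA-placebo difference alone could produce it.
- The f was set for total serum bilirubin. The documents give no effect size for the other liver tests, steatosis or RAND-36, so the percentages do not transfer to those variables.
- The splits are hypothetical, and disagreement falls if the true effect is well above the planned one.

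All 14 shells share the two-block layout, but Tables 1, 2 and 12-14 (baseline, safety and concomitant medication) raise no efficacy question, so the point is confined to Tables 3-11.

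Finally, SAP 11.3 expects a final SAP before database lock. That does not close the gap, but it leaves room to close it.

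**Conclusion.** The point holds for efficacy Tables 3-11. The plan announces an overall analysis and is sized for one, yet its shells report only stratum-by-stratum three-arm p-values, and SAP 11.3 has no method with a stratum term. At the SAP's own effect size, taken as equal in both strata with 270 evaluable, the two columns would disagree on significance in about half to two thirds of trials (49-65%) for splits from 50:50 to 80:20. The equal split, which is the most favourable to the plan, already gives 49%. The size depends on the bilirubin-based f and on the assumed split; at f = 0.32 it is 15-48%. The absence of an overall column, a stratum-adjusted comparison and an interaction test depends on neither. This should be corrected in the final SAP. It does not affect eligibility, data collection or the sample size.

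**What to change.** For each efficacy variable in Tables 3-11:

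1. Fit one whole-sample model with arm and fibrosis stratum. Report the overall stratum-adjusted arm comparison as the main result, in its own column.
2. Add an arm-by-stratum term. Report its p-value with the stratum-specific arm differences and 95% CIs. Label any within-stratum p-values as subgroup results.
3. State that a claim of a different effect by fibrosis stage rests on the interaction, not on one stratum being significant and the other not.
4. For variables now sent to Kruskal-Wallis, name a transformed or rank-based version of the same model, and fix the scale in advance.
5. Rewrite SAP 11.4 so that it agrees with the shells.

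**Cost.** SAP wording and table columns; no new data. The interaction test has low power, and there would be about 23 of them (6 liver tests, 1 steatosis measure and 8 RAND-36 domains at 2 visits: 6 + 1 + 16). Unadjusted at 0.05, about 23 × 0.05 = 1.15 false positives would be expected if no true interaction exists. Stratum differences should therefore stay descriptive.
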